7.1.1.2 Radiographic assessment method (mRUS)

Healing will be assessed on standard plain anteroposterior (AP) and lateral radiographs. For each fractured bone, four cortices are scored (1–4) and summed to yield an mRUS from 4 (not healed) to 16 (fully healed). Scoring of each cortex is defined as follows:

- visible fracture line and no callus is scored 1 (Figure 2.1)
- non-bridging callus with visible fracture line is scored 2 (Figure 2.2)
- bridging callus with visible fracture line is scored 3 (Figure 2.3)
- bridging callus with no visible fracture line is scored 4 (Figure 2.4)

The sum of the four cortices constitutes the mRUS for that bone. Based on prior work, a threshold of mRUS ≥ 11 is considered consistent with radiographic union and mRUS ≥ 13 with definite union [51].

[figure not shown]

Figure 2 - Calculation of mRUS. A cortex with visible fracture line and no callus is scored one (1), with non-bridging callus and a visible fracture line is scored two (2), with bridging callus and a fracture line is scored three (3) and with bridging callus and no visible fracture line is scored four (4). The sum of the four scores gives the mRUS.

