7.1.1.3 Radiographic healing threshold (primary endpoint)

Healing will be defined as mRUS ≥ 11 for the fractured bone with bridging callus (cortex score ≥ 3) present in at least three of four cortices, and no cortex with score of 1. For combined radius and ulna fractures, the endpoint is met when both bones meet the healing threshold on the same radiographic assessment.

This threshold operationalizes union as bridging callus in ≥ 3 cortices (consistent with established radiographic union definitions) while limiting premature classification by requiring absence of cortices with no callus.

[figure not shown]
Definite union (supportive threshold). As a supportive radiographic definition, definite union will be defined as mRUS ≥ 13 for the fractured bone, which corresponds to bridging callus in all four cortices with at least one cortex demonstrating absence of a visible fracture line (cortex score 4). This more stringent threshold is expected to occur later in the healing trajectory and will therefore be used for pre-specified sensitivity analyses of the primary time-to-healing endpoint and for descriptive comparison of healing profiles between groups, rather than as the primary event definition.

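### A total mRUS of 13 or more does not guarantee the four bridged cortices that Section 7.1.1.3 says it represents

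*Protocol*

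**What the plan says.** Section 7.1.1.2 scores four cortices per bone from 1 to 4 and adds them, so the mRUS runs from 4 to 16. The cortex scores mean:

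- 1: "visible fracture line and no callus is scored 1"
- 2: "non-bridging callus with visible fracture line is scored 2"
- 3: "bridging callus with visible fracture line is scored 3"
- 4: "bridging callus with no visible fracture line is scored 4"

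A cortex is therefore bridged only if it scores 3 or 4.

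Section 7.1.1.3 builds the primary event from the total and from the individual cortices: mRUS of at least 11, "with bridging callus (cortex score ≥ 3) present in at least three of four cortices", "and no cortex with score of 1". It then adds a supportive event: "definite union will be defined as mRUS ≥ 13 for the fractured bone, which corresponds to bridging callus in all four cortices", and the sentence goes on to require one cortex without a visible fracture line. The cortex-level conditions of the primary rule are not repeated for this event. The section describes the threshold as stricter than the primary one and expected later in healing. It assigns it to pre-specified sensitivity analyses of time to healing and to descriptive comparison of the groups. Section 7.1.1.2 attributes the cut-offs of 11 and 13 to prior work.

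**The concern.** The definition is a total, and the clause after it presents four-cortex bridging as what that total means. A total cannot carry that meaning if a low score on one cortex can be offset by high scores on the others.

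Two things would follow. First, an analyst who codes a total of at least 13 and one who codes the described condition could give the same child different event times, although both follow the same sentence. A report that repeats the clause could also claim four-cortex bridging that the films did not show. Second, if some pattern reaches 13 while failing the primary rule, the event meant to be stricter could be recorded in a bone not yet counted as healed.

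**Working it through.** **Inputs.** Four cortices, each scored 1 to 4, bridged if 3 or more (Section 7.1.1.2). Primary rule: total at least 11, at least three cortices scoring 3 or more, none scoring 1. Definite union: total at least 13, described as all four cortices bridged with at least one scored 4 (both Section 7.1.1.3).

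**Step 1: the protocol's figure, from description to total.** If every cortex scores at least 3 and one scores 4, the smallest total is 3+3+3+4 = 13. The figure of 13 is reproduced, and this direction is correct.

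**Step 2: from total to description.** The maximum is 16, so a total of at least 13 allows up to 3 points to be lost. A cortex scored 2 loses 2 points and a cortex scored 1 loses 3, so either fits. All combinations with a total of at least 13 are:

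| Scores | Total | Arrangements over four cortices | All four bridged | Meets primary rule |
|---|---|---|---|---|
| 4-4-4-4 | 16 | 1 | yes | yes |
| 3-4-4-4 | 15 | 4 | yes | yes |
| 3-3-4-4 | 14 | 6 | yes | yes |
| 2-4-4-4 | 14 | 4 | **no** | yes |
| 3-3-3-4 | 13 | 4 | yes | yes |
| 2-3-4-4 | 13 | 12 | **no** | yes |
| 1-4-4-4 | 13 | 4 | **no** | **no** |

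Unordered, 3 of 7 combinations contain a non-bridged cortex. Ordered, there are 1+4+6+4+4+12+4 = 35 patterns, of which 4+12+4 = 20 (57%) contain a non-bridged cortex and 1+4+6+4 = 15 (43%) match the description.

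**Step 3: by total.** At exactly 13, 12+4 = 16 of 20 ordered patterns include a non-bridged cortex; at 14, 4 of 10; at 15 and 16, none. Used alone, the lowest total that guarantees four bridged cortices is 15.

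**Step 4: nesting.** 2-3-4-4 and 2-4-4-4 satisfy the primary rule: the total exceeds 11, three cortices score at least 3, and none scores 1. 1-4-4-4 has a total of 13 and three bridged cortices but fails because one cortex scores 1. If cortex scores do not fall over time, a bone showing 1-4-4-4 cannot have met the primary rule earlier, so definite union would be dated before healing.

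**Step 5: possible repairs.** With every cortex at least 3 and one equal to 4, 15 ordered patterns (4 of the 7 combinations) qualify, and all meet the primary rule. With a total of at least 13 plus the primary rule's cortex conditions, 35 − 4 = 31 ordered patterns (6 of 7) qualify. Nesting is restored, but 12+4 = 16 of those 31 still have one non-bridged cortex.

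**The case against.** The best defence is that the intended meaning is already in the sentence, since it names four bridged cortices and one scored 4, and that the analysis plan still to be prepared (Section 8.3) can state the rule. The intention is indeed legible. But the sentence offers the condition as a consequence of the total, which is false, and the protocol itself fixes this event, so the text needs correcting on either reading.

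Three stronger readings are tempting, and the documents do not support them.

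- *A reader might infer that most bones called definitely united would have an unbridged cortex.* A majority appears only when cortices are told apart (20 of 35); by combination it is a minority (3 of 7). Both counts weight every pattern equally, and the documents give no distribution of cortex scores.
- *A reader might infer that the two events are generally out of order.* Only 1-4-4-4 breaks the nesting: three cortices with no visible fracture line beside one with no callus. Nothing in the documents says how often that occurs, and it may be rare.
- *A reader might infer that the safety assessment of the flexible nail or the main conclusion is compromised.* Visit scheduling (Sections 6.2.8 and 6.2.9) and the sample size (Section 8.2) use 11. The pause criteria (Section 19.1) use refracture rate and mean time to radiographic healing. The primary event has its own cortex conditions. The definite-union rule is the same in both arms and is read by blinded assessors, and no direction of bias between arms can be shown.

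It is also fair to say that 13 is presented as a cut-off from prior work, so the sponsor may have reason to keep it for comparability.

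**Conclusion.** The stated equivalence is false on the protocol's own scale. A total of 13 or more is necessary for the described condition but not sufficient: 3 of 7 combinations (20 of 35 ordered patterns) reach it with a non-bridged cortex. One combination, 1-4-4-4, also fails the primary rule, so definite union is not strictly a subset of healing.

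This rests only on the scoring definitions in Section 7.1.1.2 and the two rules in Section 7.1.1.3. How many children would be classified differently cannot be estimated from the document. The consequence is limited to the sensitivity analyses and descriptive comparisons that use the threshold. It is a small defect in a supportive definition, but it leaves two possible codings of a pre-specified event and is worth correcting before readings begin.

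**What to change.** In Section 7.1.1.3 and the scoring manual, define definite union by cortex scores: every cortex at least 3 and at least one cortex equal to 4, in all fractured bones on the same radiographic assessment. This forces an mRUS of at least 13 and makes definite union a true subset of healing.

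If the sponsor prefers to keep the cited total of 13, delete the clause equating it with four bridged cortices and add the primary rule's cortex conditions. That restores nesting, but the event then does not certify four-cortex bridging and should not be reported as if it did.

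Either change is a short text edit. Cortex scores are already part of the reading (Sections 7.1.1.2 and 7.1.1.5), so no additional films or readings are needed. The downside is that some children will meet definite union later than under the total alone; under the second option this applies only to a bone showing 1-4-4-4.

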7.1.1.4 Blinding of radiographs via standardized image masking

Bioabsorbable intramedullary nails are largely radiolucent, with only a radiopaque tricalcium phosphate tip, whereas titanium nails are inherently radiopaque. To ensure blinded radiographic outcome assessment across treatment groups, all postoperative radiographs will be de-identified and digitally masked prior to review. Using image-editing software, visible radiopaque implant components will be concealed, while preserving full visibility of the fracture region, cortical outlines, and callus formation (Figure 3). All patient identifiers and acquisition metadata will be removed, and images will be assigned a study-specific ID and a non-revealing time point label only.

Image manipulation will be performed by a member of the research team who is not involved in postoperative clinical assessment, outcome evaluation, or statistical analysis, and who will have no role in adjudication of radiographic endpoints. Masking procedures will be documented to ensure consistency. All manipulated images are stored outside PACS. All original unaltered radiographs are stored in the hospital's PACS.

Original follow-up radiograph

Edited radiograph with implant concealed

Figure 3 – Example of original and edited radiograph to blind the assessor to the implant.

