6.2.7 Visit 2 (4 weeks)

- Assessment for any adverse events (AEs) since the previous visit, including documentation and reporting as applicable
- Radiographs

- Cast removal for the bioabsorbable intramedullary nail (BIN) group, if applicable
- Clinical examination and outcome assessments as described in Section 7
- Source data verification and entry into the eCRF
- Scheduling of the next visit
- Appointment for the next visit

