Unblinding may be performed only when knowledge of the allocated implant is deemed necessary for urgent clinical management. Emergency unblinding will be performed by the PI, documented in the eCRF (date, reason, person unblinded, and who was informed), and reported to the sponsor.

6.3.7.4 *Blinded groups*

The following parties will be blinded to treatment allocation:

- Participants and parents will be blinded to implant type. Families will be informed preoperatively that postoperative immobilization duration may vary between 2–4 weeks based on radiographic assessment, and they will not be informed that immobilization duration differs systematically between the randomized interventions. As the implant is not externally visible after cast removal and implant-specific radiographic features are concealed for research assessments (Section 7.1), there is no direct method for participants and parents to identify allocation during follow-up.
- Postoperative ward/clinic caregivers and staff involved in routine care.
- Outcome assessors and data collectors, including:
 - Clinicians performing follow-up assessments
 - Radiologists and orthopedic surgeons reviewing radiographs (using edited, de-identified images; Section 7.1)
 - Occupational therapists / hand therapists performing functional assessments
- Statistician/data analyst, who will receive a dataset with groups coded (e.g., Group A/B) and will remain blinded until database lock and completion of the prespecified primary analysis.

6.3.7.5 *Preventing inadvertent unblinding*

To reduce inadvertent disclosure, the study team will implement the following safeguards:

- Use of standardized note templates for postoperative notes and discharge summaries.
- Clear instruction to staff not to document implant type in routine follow-up notes that are accessible to blinded parties.
- If implant type must be referenced for clinical reasons before planned unblinding, it will be documented and handled according to the emergency unblinding procedure.

6.3.7.6 *Assessment of blinding success*

Blinding success will be assessed immediately prior to participant/parent unblinding at the 6-month follow-up visit. Participants/parents will be asked to guess the allocation (“bioabsorbable”, “titanium”, or “don’t know”) and if they specify an implant, they will be asked why they chose that implant. The proportion of correct guesses and reasons (and proportion choosing “don’t know”) will be summarized by randomized group.

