6.3.8 **Postoperative care**

Following surgery, a circumferential above-elbow cast is applied. The patient will be observed and/or admitted to the pediatric ward as clinically indicated until the effect of the peripheral nerve block (PNB) has subsided and discharge criteria are met. The patient is encouraged to mobilize the shoulder and fingers as soon as possible and to keep the arm elevated for the first few days. Daily activities may be resumed as tolerated. Return to sports will be discussed individually at the 3-month follow-up visit in accordance with standard of care.

Before discharge, a standardized discharge and follow-up plan will be provided.

In the investigational group (BIN), all patients will remain in a cast for 4 weeks. In the comparator group (TEN), cast removal is planned at the 2-week follow-up visit.

Any postoperative care not specifically described in this protocol will be provided according to standard of care at the study site and described in a specific SOP.

6.3.9 **Non-operative treatment**

If the fracture is successfully reduced by closed manipulation prior to skin incision and is considered eligible for non-operative management, the patient will be included in an exploratory prospective non-operative cohort. Based on our pilot experience, the proportion of successful closed reductions is anticipated to be approximately 15%.

6.3.9.1 *Eligibility for non-operative management*

Fractures are considered eligible for non-operative treatment when, after reduction, the fracture is:

- not displaced by more than 50% of the bone width, and
- not angulated by more than 10° in any plane.

The decision to manage the fracture non-operatively is at the treating surgeon’s discretion and follows standard of care.

6.3.9.2 *Follow-up and conversion to surgery*

Participants in the non-operative cohort will have a radiographic follow-up at 1 week. Thereafter, they will follow the same follow-up schedule and outcome assessments as the randomized groups (Section 6.2). Fracture healing is typically sufficient to allow cast removal after 6–8 weeks.

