12.2 Imaging data

Radiographs are stored securely in the hospital's Picture Archiving and Communication System (PACS). For the blinding process, radiographs provided for outcome assessment will be de-identified and will not contain patient-identifiable information. The images will be labeled only with the participant's numeric study identifier code.

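### As written, the masking and labelling of radiographs may let the readers of the primary endpoint infer the allocated implant

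*Protocol*

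**What the plan says.** Protocol 7.1.1.4 states the difficulty itself: "Bioabsorbable intramedullary nails are largely radiolucent, with only a radiopaque tricalcium phosphate tip, whereas titanium nails are inherently radiopaque". Its remedy is to de-identify all postoperative films and edit them so that "visible radiopaque implant components will be concealed, while preserving full visibility of the fracture region, cortical outlines, and callus formation". Section 6.3.7.2 repeats the rule in similar terms. Neither section says that the edited area must look the same in both arms, and neither mentions the cast.

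On casting, section 6.3.8 says "In the investigational group (BIN), all patients will remain in a cast for 4 weeks" and plans removal in TEN at the 2-week visit. Films are scheduled at both the 2-week and the 4-week visit (6.2.6, 6.2.7, 7.3). The 4-week list places radiographs just before the item "Cast removal for the bioabsorbable intramedullary nail (BIN) group, if applicable"; the 2-week list has the same order for TEN.

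On labels, 7.1.1.4 says "images will be assigned a study-specific ID and a non-revealing time point label only", whereas 12.2 says "The images will be labeled only with the participant's numeric study identifier code".

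Readers see the films in random order and without clinical data. Two read independently, and a third adjudicates if they cannot agree (7.1.1.5). The only check of blinding is in families: "Participants/parents will be asked to guess the allocation" (6.3.7.6).

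**The concern.** The mRUS asks a reader to judge whether callus bridges and whether a fracture line is still visible (7.1.1.2). Surgeons and operating room staff know the implant (6.3.7), so masked reading is the main protection for the primary endpoint. The protocol also states an expectation that readers may share: the more flexible BIN could in theory delay union (section 2).

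If the edited area, a cast or a linked label lets a reader guess the arm, that expectation can enter the date of the first film read as healed. Bias in favour of BIN would raise the chance of a false claim of non-inferiority. Bias against BIN would cost power. Agreement statistics between two readers who see the same cues would not reveal either, and no data on the readers' guesses are planned.

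**Working it through.** **1. Mask.** Rule: conceal what is visibly radiopaque (7.1.1.4).
- TEN: the nail is radiopaque, so the edit follows the nail, up to its removal at 6 to 12 months (6.2.14).
- BIN: only the tip is radiopaque, so the edit is confined to the tip.
- Result: applied literally, the footprint differs by arm on the films that decide the endpoint.

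**2. Cast on film.** Planned durations are 2 weeks (TEN) and 4 weeks (BIN).

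| Order at the visit | Week 2 film | Week 4 film |
|---|---|---|
| Film before removal | both in cast | BIN in cast, TEN not |
| Film after removal | BIN in cast, TEN not | neither in cast |

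Under either uniform order, one scheduled film separates the arms. The order of the bullets in 6.2.6 and 6.2.7 suggests the first row, but no sequence is stated in words.

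**3. How much the cast cue can do by itself.** With the planning values of mean 8 and SD 3 weeks (8.2.2) and a normal distribution, the share united is Φ((4 − 8)/3) = 9.1% by week 4 and Φ((2 − 8)/3) = 2.3% by week 2. Few event times turn on those films, so the cue matters mainly if it can be carried to later films of the same child.

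**4. Label.** A participant code (12.2) allows that link despite random order. The study-specific ID in 7.1.1.4 could be either image-level or participant-level. The two sections have to be reconciled.

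**5. Design figures.** These are not in dispute. n per group = 2 × [SD × (z₀.₉₇₅ + z₀.₉₀)/Δ]² = 2 × [3 × (1.960 + 1.282)/3]² = 21.01, rounded up to 22. Then 22/0.90 = 24.4, rounded up to 25 per group and 50 in total, as in 8.2.7. Planned enrolment is 30 per group.

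**6. Illustration of size.** The protocol gives no figure for reader bias, so the fraction f below is an assumption. Films are 2 weeks apart (8.3.6). If the first healed reading moves by one visit in a fraction f of one arm, the bias is b = 2f weeks. With a normal difference in means and 30 per group, SE = 3 × √(2/30) = 0.775 weeks.
- One-sided type I error with bias favouring BIN: Φ(b/SE − 1.96).
- Power at no true difference with bias against BIN: Φ((3 − b)/SE − 1.96).

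| f (assumed) | b (weeks) | Type I error | Power |
|---|---|---|---|
| 0 | 0 | 2.5% | 97.2% |
| 10% | 0.2 | 4.4% | 95.1% |
| 25% | 0.5 | 9.4% | 89.8% |
| 50% | 1.0 | 25.2% | 73.3% |

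With 22 per group, the type I error is 4.1%, 8.0% and 19.6% in the last three rows.

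**The case against.** The protocol takes blinding seriously. All postoperative films in both arms are masked under a documented procedure headed as standardized. The person who edits them has no role in outcome assessment. Metadata are removed, readers are calibrated and follow a scoring manual, and disagreements are adjudicated. The example of an edited film (Figure 3) is not shown in the text at hand, so an equal mask in practice cannot be excluded. These protections make a systematic shift of a whole visit less likely. They do not remove a visual cue that every reader sees, and the wording still requires no equal edit.

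A reader might infer more than the text supports:
- **That readers will in fact be unblinded.** The text creates the possibility and no more.
- **That BIN children are certainly filmed in cast at 4 weeks.** This rests on bullet order; under the other order the asymmetry moves to week 2. Cast removal is also qualified as applying only where applicable. The non-operative cohort has a longer cast as well, so a cast on film is not unique to BIN among all study participants, though it still separates BIN from TEN.
- **That the protocol fixes participant-linked reading.** Only 12.2 points that way, and it concerns de-identification.
- **That every film to 6 months is at risk.** Once union is recorded, later films cannot change the event time.

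The lack of a reader guess is not an error; adding one is good practice.

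**Conclusion.** The concern holds as a risk created by the wording. The masking rule, followed as written, gives edits that differ by arm on the films that determine the primary endpoint, and nothing in the protocol requires otherwise. The cast difference adds a second cue on one scheduled film, and the label in 12.2 could carry either cue across a child's films. The direction and size of any resulting bias are unknown. The range of 0.2 to 1.0 week rests wholly on the assumed 10% to 50% of one arm shifted by one visit, and on a normal approximation in place of the planned interval-censored model. The correction is worth making before enrolment because it is cheap and the films cannot be read afresh by readers who have already seen the cues.

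**What to change.** 1. In 7.1.1.4, require one identical canal-shaped mask footprint on every nailed bone in both arms, whatever is visible on the film. Size it to the canal and not to the nail, and keep the cortices and callus clear. Crop or mask any cast shadow outside the bone where feasible.
2. Reconcile 7.1.1.4 and 12.2 so that readers see only a random image-level ID (one per AP and lateral pair, since the score needs both views). The person who does the masking holds the link to the participant.
3. Optionally, add a field in which each reader records a guess of the allocation, reported by arm.

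Cast duration and the order of film and cast removal stay as they are; this point proposes no change to either.

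Cost: wording in two sections and the imaging SOP and, if wanted, one field on the reading form. No extra films or staff are needed. The downside is that some canal area on BIN films is hidden; the score is taken from the cortices, so the loss should be small if the footprint stays inside the canal.
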